6.11 Efficacy Analysis

Efficacy evaluations will be performed based on both the Intent-to-Treat Set and the Efficacy Evaluable Set.

6.11.1 Efficacy Variables for Analysis

The primary efficacy variable is:

- Progression-free survival (PFS) as assessed by the Investigator

The key secondary efficacy variables are as follows:

- Overall response rate (ORR) as assessed by the Investigator;
- Change in Skindex-29 score from baseline through the 6-month assessment;
- Change in FACT-G total score from baseline through the 6-month assessment;
- Change in EQ-5D-3L index score from baseline through the 6-month assessment.

Other secondary efficacy variables include:

- Progression-free survival (PFS) as assessed by IR;
- Overall response rate (ORR) as assessed by IR;
- Best overall response;
- Duration of response (DOR);
- Time to response (TTR);
- Overall response rate in the crossover portion of the trial;
- Changes from baseline in Skindex-29, FACT-G, and EQ-5D-3L at other timepoints;
- Changes from baseline in Pruritus Evaluation (Likert scale & Itchy QoL).

An overall response is defined as a CR or PR at any time during the treatment period prior to progression/relapse, if applicable. The best overall response is the best response reported across all visits during the treatment period prior to a progression/relapse, if applicable.

The exploratory efficacy variables include:

- Overall survival (OS);
- Time to treatment failure (TTF)

Disease status will be assessed every 4 weeks in skin and blood. In the first year of treatment, response in lymph nodes and viscera and the overall global composite score will be documented every 8 weeks. After the first year, response in the lymph nodes and viscera and the overall global composite score will be documented every 16 weeks. Additionally, if

clinical progression is noted, efficacy assessments are performed to fully document disease progression.

These assessments will be compared with the baseline assessment to determine response. Subjects will be evaluated for response in each compartment and overall. For any time-to-event endpoints (e.g., PFS), the date of disease progression will be determined by both the on-site Investigator's assessment and the IR.

6.11.1.1 Definition of Primary Efficacy Variable

The primary efficacy variable is progression-free survival (PFS) based upon the assessment by the Investigator, defined as the time from the day of randomization to a treatment arm until documented progression or death due to any cause.

Documented disease progression includes disease progression in any compartment based on the Investigator's assessment per CTCL response criteria or documented disease progression reported during the follow-up period. The date of progression will be the earliest date at which documented disease progression can be declared.

For subjects who exhibit conditions of disease progression, but continue on the study due to a questionable clinical impression as described in Section 3.2.2.3, the subject is not considered to have progressed unless disease progression is confirmed at least 4 weeks after the date of the initial questionable disease progression. In this case, the initial date will be used as the date of disease progression.

Subjects who died without a reported prior progression will be considered to have progressed on the day of their death.

The definition of censoring date will be as follows:

- In the event that a randomized subject withdraws from the study for any reason before documented progression, the time from the day of randomization to the last post-baseline tumor assessment from any compartment (skin, blood, bone marrow, lymph node, and viscera) will be used as a censored time point.
- For subjects who are randomized to a treatment arm but have an unknown baseline assessment for a compartment, the PFS time will be censored at the randomization date if there is no post-baseline tumor assessment for that compartment or if there is any evidence of lymphoma in that compartment at post-baseline evaluation.

- For subjects randomized to a treatment arm but withdrawing prior to the first post-baseline tumor assessment for any reason other than disease progression, the PFS time will be censored at the last documented visit.
- For subjects who initiate a new anticancer therapy (including crossover to KW-0761) in the absence of a PFS event, the PFS time will be censored at the last tumor assessment (from any compartment) prior to the start of the new anticancer therapy.
- For subjects not known to have died or have documented progression as of the end of the study, the PFS time will be censored at the date of the last post-baseline tumor assessment (from any compartment).

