7.5 Follow-Up

All subjects will be contacted by telephone every 30 days (± 7 days) up to 90 days after the last dose of study medication or initiation of alternative therapy, whichever comes first, to confirm any new onset AEs or toxicities. If a subject who has received KW-0761 undergoes a stem cell transplant at any time during or after the 90-day follow-up period, AEs/SAEs should be documented from the transplant procedure through 180 days post-transplant.

During follow-up, medications used to treat an AE and those that are temporally associated with the AE and may have a causal relationship will be recorded. In all subjects who cross

over from vorinostat to KW-0761, the causality should be assessed for both drugs for 30 days after vorinostat was stopped (or later if the event is considered to be related to vorinostat).

- After a subject who receives KW-0761 goes off study, if CD4 and CD8 counts are less than $200/\text{mm}^3$ at the End-of-treatment visit, they will be followed every 3 months (± 14 days) until they return to at least $200/\text{mm}^3$, initiation of alternative therapy or 1 year, whichever comes first.
- In the absence of disease progression, all subjects or their referring physicians will be contacted every 3 months (± 14 days) until documented disease progression or death, or initiation of alternative therapy.
- All subjects or their referring physician will be contacted every 3 months (± 14 days) to ascertain survival status.
- For all subjects who have received KW-0761, subsequent stem cell transplant information should be recorded in a separate CRF provided by the Sponsor. For subjects who undergo transplant, concomitant medications and AEs/SAEs should be documented through 180 days post-transplant on the CRFs provided.
- All follow up information and attempts to obtain follow up information should be documented in the subject's source record.

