6.3 Determination of Sample Size

Since the primary endpoint is PFS, the reference median PFS for vorinostat is assumed to be 169 days.⁵ The median PFS for KW-0761 therapy is targeted for 254 days, a 50% improvement over this reference median. For a 24-month accrual and 12 month follow-up on the last subject dosed, Table 10.3-1 of the protocol gives the power and the number of PFS events required to show superior PFS for KW-0761 therapy over vorinostat at the one-sided

0.025 significance level. The Intent-to-Treat (ITT) set is used for this primary analysis. The same analysis conducted using the Efficacy Evaluable set is considered secondary.

Under these assumptions, for the ITT population, a total of 255 PFS events will give 90% power. For this study, the final primary analysis comparing PFS between treatment groups will not be conducted until 255 PFS events occur or until a maximum of 24 months after the last randomized subject's first dose, whichever comes first. In the event that the study is stopped prior to 255 PFS events being observed, the primary test will be performed at less than 90% power under the current assumptions according to Table 10.3-1 in the protocol.

Each of these calculations used a log-rank test to compare the two survival curves. Sample size calculations were computed using SAS software version 9.3 using PROC POWER, Twosamplesurvival test = logrank.

The total sample size of 288 represents the approximate number of subjects that may be necessary for 255 PFS events to occur within the projected 36 months of the trial. If a 10% inflation factor is applied to this total (about 29 subjects) to take into account those subjects that may be lost to follow-up prior to documented progression, a total of 317 enrolled subjects may be necessary in order to observe 255 PFS events.

The observed rates of PFS events, recruitment, and drop-outs will be monitored throughout the study and may be used to alter the number of sites, the accrual period, and the follow-up period to achieve the required 255 PFS events in a timely manner. If the 255 PFS events are not observed within 36 months from the start of enrollment the study will be stopped at approximately 24 months after the last randomized subject's first dose.

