6.11.2 Efficacy Analysis Methodology

6.11.2.1 Analysis of Primary Efficacy Variable

The primary comparison of progression-free survival between KW-0761 and vorinostat will be performed on the ITT set based upon the results of the on-site Investigator's assessment using a stratified Log-rank test at the one-sided 2.5% significance level. Stratification is done by disease type (MF or SS), disease stage (IB/II or III/ IV), and region (U.S., Japan, and Rest of World). A Cox proportional hazard model with treatment, disease type, disease stage, and region (U.S., Japan, and Rest of World) as covariates will be used to assess the magnitude of the treatment difference in PFS. The hazard ratio along with the 95% confidence interval obtained from the Cox proportional hazard model will be presented. Additional analyses may be performed adjusting for treatment and other baseline characteristics.

The median PFS and the 2-sided 95% confidence interval for each treatment will be estimated using the Kaplan-Meier survival analysis methods. Kaplan-Meier estimate of PFS rates and the corresponding 95% confidence interval will also be provided for each treatment arm by 6 months intervals. Plots of the Kaplan-Meier estimate of the survival distribution function over time for PFS will be presented by treatment arm.

The primary analysis of PFS will be performed when 255 total PFS events have been observed or 24 months after the last randomized subject's first dose, whichever comes first.

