<<Programming Note: For Itchy QoL, Symptoms scale includes questions 1 to 6; Functioning scale includes questions 7 to 13; Emotions scale includes questions 14 to 22.>>

The following listings will have similar layout as Listing 16.2.6.31 and Listing 16.2.6.32:

Listing 16.2.6.33
Pruritus Evaluation - Itchy QoL Assessment During Crossover Portion
Subjects Who Are Randomized to Vorinostat and Crossed Over to KW-0761

Listing 16.2.6.34
Pruritus Evaluation Score During Crossover Portion
Subjects Who Are Randomized to Vorinostat and Crossed Over to KW-0761

Listing 16.2.6.35
 Skin Biopsy During Randomized During Pre-Treatment and Treatment Period

Trt Arm Subject	Visit	Biopsy Performed?	Collection Date	Result	Reason for Skin Biopsy
Vorinostat					
xxx-xxx	xxxxxxx	Yes	YYYY-MM-DD	xxxxxxx	xxxxxxxxxxxxxxxxxxxxxxxxxxxx
	xxxxxxx	Yes	YYYY-MM-DD	xxxxxxx	xxxxxxxxxxxxxxxxxxxxxxxxxxxx
xxx-xxx	xxxxxxx	Yes	YYYY-MM-DD	xxxxxxx	xxxxxxxxxxxxxxxxxxxxxxxxxxxx
	xxxxxxx	Yes	YYYY-MM-DD	xxxxxxx	xxxxxxxxxxxxxxxxxxxxxxxxxxxx
xxx-xxx	xxxxxxx	Yes	YYYY-MM-DD	xxxxxxx	xxxxxxxxxxxxxxxxxxxxxxxxxxxx
	xxxxxxx	Yes	YYYY-MM-DD	xxxxxxx	xxxxxxxxxxxxxxxxxxxxxxxxxxxx
KW-0761					
xxx-xxx	xxxxxxx	Yes	YYYY-MM-DD	xxxxxxx	Other: xxxxxxxxxxxxxxxxxxxxxxxx
	xxxxxxx	Yes	YYYY-MM-DD	xxxxxxx	Other: Skin Rash: xxxxxxxxxxxxxxxxxxxxxxxx

The following listing will have a similar layout as Listing 16.2.6.35:

Listing 16.2.6.36
Skin Biopsy During Crossover Portion
Subjects Who Are Randomized to Vorinostat and Crossed Over to KW-0761

Listing 16.2.6.37
 Survival Status

Trt Arm Subject	Date of Contact	Method of Contact	New Anti- Cancer Therapy?	Date of Therapy	Disease Progression?/ Date	Method of Confir- mation	Subject Alive?/Date of Death	Primary Cause of Death	Autopsy Conducted?/ Sig. Findings
Vorinostat									
xxx-xxx	xxxxxxxx	xxxxxxxx	Yes/Specify	YYYY-MM-DD	Yes/YYYY-MM-DD	xxxxxx	Yes		
	xxxxxxxx	xxxxxxxx	No		No		No/YYYY-MM-DD	xxxxxxxx	No
xxx-xxx	xxxxxxxx	xxxxxxxx	No		No		Yes		
	xxxxxxxx	xxxxxxxx	No		Yes/YYYY-MM-DD	xxxxxx	Yes		
xxx-xxx	xxxxxxxx	xxxxxxxx	No		No		Yes		
	xxxxxxxx	xxxxxxxx	No		No		No/YYYY-MM-DD	xxxxxxxx	
KW-0761									
xxx-xxx	xxxxxxxx	xxxxxxxx	Yes/Specify	YYYY-MM-DD	Yes/YYYY-MM-DD	xxxxxx	Yes		
	xxxxxxxx	xxxxxxxx	No		No		No/YYYY-MM-DD	Other: xxxxxxxx	Yes/xxxxxxxx

Listing 16.2.7.1
 Adverse Events During During Pre-Treatment and Randomized Treatment Period

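### For subjects who stop treatment without progression, the primary PFS uses the 3-monthly follow-up contact when it reports progression but not when it reports none, so time at risk depends on outcome

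*SAP*

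**What the plan says.** **Events.** SAP 6.11.1.1 defines documented progression as progression in any compartment by the investigator's assessment "or documented disease progression reported during the follow-up period". Death without prior progression counts as an event on the day of death.

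**Censoring.** For subjects not known to have died or progressed by the end of the study, "the PFS time will be censored at the date of the last post-baseline tumor assessment (from any compartment". The rules for withdrawal and for new anticancer therapy (including crossover) also go back to the last tumor assessment. A subject with no post-baseline assessment is censored at the last documented visit. No rule uses the last contact at which the subject was progression-free.

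**Follow-up.** SAP 5.1 schedules skin and blood assessments every 4 weeks during treatment. The end-of-treatment procedures named in protocol 5.5 are safety procedures. After that, protocol 7.5 says: "In the absence of disease progression, all subjects or their referring physicians will be contacted every 3 months", until progression, death or alternative therapy. Protocol 7.6 is the exception: subjects who stop after a complete response (CR) keep scheduled mSWAT, flow cytometry and CT.

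**Data.** SAP Listing 16.2.6.37 holds each contact date, the field "Disease Progression?/ Date", the method of confirmation, and the date of any new anticancer therapy.

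**The concern.** Censoring at the last tumor assessment is coherent when events also come only from assessments. Here events may come from contacts as well, while censoring may not. Whether a subject's off-treatment time enters the risk set then depends on what happened during that time, which is not independent censoring.

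The arms may also differ in how much this matters. A vorinostat subject who stops for intolerance may cross over and is then censored, so may have little contact follow-up. A KW-0761 subject who stops for rash or infusion reaction has no crossover and stays in contact follow-up until other therapy starts. At stake are the primary hazard ratio, its test, and both reported medians.

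**Working it through.** **1. The plan's own figure.** SAP 6.11.2.1 tests PFS "using a stratified Log-rank test at the one-sided 2.5% significance level". SAP 6.3 gives the other inputs: "the reference median PFS for vorinostat is assumed to be 169 days", with 254 days as the KW-0761 target. So HR = 169/254 = 0.665 and ln HR = -0.407.

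Events (Schoenfeld, 1:1) = 4 × (1.960 + 1.282)² / 0.407² ≈ 254. The SAP says "a total of 255 PFS events will give 90% power"; at 255 events the power is 0.902. Uniform 24-month accrual plus 12 months gives event probabilities of 0.929 and 0.840 (mean 0.885), so N = 255/0.885 ≈ 288. The sample size reproduces and is not in question.

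**2. Two subjects under the rule.** Both stop for toxicity at month 3 and have no CR. A contact reports progression for one at month 9. For the other, every contact to month 15 is negative.

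| Rule | Subject 1 | Subject 2 | Events per subject-month |
|---|---|---|---|
| SAP 6.11.1.1 | event, 9 | censored, 3 | 1/12 |
| Censor at last negative contact | event, 9 | censored, 15 | 1/24 |
| Drop follow-up progressions | censored, 3 | censored, 3 | 0/6 |

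The second and third rules each use one source for both outcomes. The first does not.

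**3. Size.** The documents give neither the share stopping without progression nor the time to new therapy, so both are assumed: 10-30% of subjects per arm, and medians of 30-180 days. PFS and stopping times are exponential, assessments are every 28 days on treatment, contacts are every 91 days afterwards, and follow-up is complete. Deaths are not modelled separately. There are 200,000 subjects per arm, and HR is the ratio of events per person-time. V is vorinostat, K is KW-0761.

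| Stopping V/K | Median days to new therapy V/K | SAP medians V/K | SAP HR | HR, follow-up PD dropped | HR, last-contact rule |
|---|---|---|---|---|---|
| 20/20% | 180/180 | 161/243 | 0.663 | 0.662 | 0.663 |
| 30/30% | 180/180 | 157/236 | 0.665 | 0.663 | 0.665 |
| 30/30% | 30/180 | 158/237 | 0.688 | 0.662 | 0.648 |
| 30/15% | 180/180 | 157/246 | 0.624 | 0.653 | 0.649 |
| 30/15% | 30/180 | 158/247 | 0.651 | 0.659 | 0.640 |
| 15/30% | 180/180 | 165/236 | 0.706 | 0.673 | 0.677 |
| 15/30% | 30/180 | 164/235 | 0.720 | 0.673 | 0.672 |

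An extreme case has 30% stopping in each arm, immediate vorinostat crossover, and 180 days to other therapy on KW-0761. Separate runs of it gave SAP-rule HRs of about 0.70 to 0.74, and 1.07 to 1.09 with no true difference.

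**4. Error rates.** These use 4,000 trials of 158 + 159 subjects, one-sided 0.025 in favor of KW-0761.

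| Stopping V/K; days V/K | Type I: SAP | Follow-up PD dropped | Last contact |
|---|---|---|---|
| 20/20%; 180/180 | 0.025 | 0.024 | 0.025 |
| 30/15%; 180/180 | 0.078 | 0.037 | 0.037 |
| 30/15%; 30/180 | 0.047 | 0.033 | 0.056 |
| 15/30%; 180/180 | 0.004 | 0.017 | 0.018 |
| 15/30%; 30/180 | 0.006 | 0.023 | 0.024 |

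In the two 15/30% rows, power is 0.77-0.83 under the SAP rule, 0.85-0.87 with follow-up progressions dropped, and 0.89-0.90 under the last-contact rule.

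**The case against.** **Planned checks exist.** Sensitivity Analysis 1 (SAP 6.11.2.2) removes follow-up progressions. PFS by independent review is also analyzed, and the reviewer's data package in SAP 5.1.4.1 lists radiology, mSWAT, flow cytometry and date of death but no contact reports. Both are useful, but neither changes the primary estimate or isolates this effect. Sensitivity Analysis 1 also excludes deaths more than 8 weeks after the last assessment, and independent review changes the assessor. Sensitivity Analyses 2 and 3 keep follow-up progressions as events.

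**The evidence differs in quality.** A follow-up event must be documented, and the listing records how it was confirmed. A negative contact may be a telephone report from the subject or the referring physician. Protocol 10.3 itself specifies censoring at the last tumor assessment on withdrawal. This is a fair reason for caution, and it counts equally for dropping follow-up progressions from the primary analysis. It does not justify using contacts in one direction only.

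**The effect can be small.** With medians of 30 and 60 days to new therapy and equal stopping of 10%, 20% or 30%, the HR under the SAP and last-contact rules was 0.681/0.678, 0.677/0.671 and 0.671/0.662. The plan's only related figure is 10% loss before documented progression, which is not a rate of stopping treatment without progression. Immediate crossover is also extreme, since protocol 5.3 asks for dose reduction first and normally a 2-week washout. This stands.

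**A simple last-contact rule is not always better.** With 30/15% stopping and early vorinostat switching, its type I error was 0.056 against 0.047 as written. Subjects who start new therapy before their first contact remain treated asymmetrically. This stands, and the fix below allows for it.

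**Conclusion.** The asymmetry is in the text. For subjects who stop without progression and are not in CR follow-up, off-treatment time enters for those who progress or die but normally not for those who stay event-free. On the simulated assumptions this shortens the medians by up to about 12 and 19 days. It can move the HR either way, from about 0.62 to 0.74 against 0.665, when stopping or time to new therapy differs by arm. When the arms are alike, the HR stays at 0.66-0.67 and, in the 20% stopping case tested, type I error is 0.025.

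A reader might infer two stronger things. One is that off-treatment time counts only for subjects who progress. That goes too far: deaths count, CR subjects keep scheduled assessments, and the SAP censors at the last post-baseline assessment, so an unscheduled off-treatment one would count too. The other is that the bias works against KW-0761 and costs power. That happens in some scenarios, but with more stopping on vorinostat the HR falls to 0.62 and type I error rises to 0.078. Without stopping rates the documents do not fix a direction.

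**What to change.** In SAP 6.11.1.1, make the event and censoring sources match. If follow-up progressions remain primary events, amend the withdrawal, new-therapy and end-of-study rules for subjects off treatment with no progression or death:

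- Censor at the last follow-up contact recording no progression, or at the last tumor assessment if that is later.
- If new anticancer therapy has started, censor at its start date, provided the contact reporting it records no earlier progression. This covers subjects who switch before their first contact. This tightened rule was not itself simulated.

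Also add a sensitivity analysis that drops follow-up progressions but keeps all deaths, that is, Sensitivity Analysis 1 without the 8-week limit. It still credits off-treatment time to subjects who die, so its purpose is to isolate the effect of follow-up progressions.

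The cost is SAP wording and a derivation from Listing 16.2.6.37, with no new visits or data. The downsides are that negative contacts are softer evidence than tumor assessments, and that the rule departs from protocol 10.3. SAP Section 1 requires substantial differences from the protocol to be identified, so the departure should be stated.

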5.3 Cross-over to Study Drug KW-0761

Subjects who have received 2 full treatment cycles and demonstrate progression of disease on treatment with vorinostat at the 8 week (Cycle 2, Day 26-28) assessment, or anytime thereafter, may cross over to treatment with KW-0761 after discussion with Medical Monitor or designee and receipt of approval for cross over from KKD. Investigators should strive to maintain subjects on treatment for at least the 8 week period, adjusting the dose of vorinostat as needed for toxicities in order to allow sufficient time to see effect. In cases where a subject's disease progresses rapidly (i.e., prior to 8 weeks), the Medical Monitor or designee should be contacted and may consider the possibility of early crossover, if appropriate for that subject. All subjects must undergo the full extent of disease evaluations (including CT scanning) to document PD prior to crossover.

There must be at least 2 weeks between the last dose of vorinostat and first dose of KW-0761. Subject must continue to meet eligibility criteria outlined in Section 3.4 and all toxicity must have resolved to Grade \leq 1 or to baseline in order to receive KW-0761. Treatment with KW-0761 should commence with procedures outlined for Day 1 in Table 1 of Study

Procedures for the first treatment cycle. In cases where a subject's disease progresses rapidly, the Medical Monitor or designee should be contacted and may consider initiation of treatment with KW-0761 prior to the 2-week washout period.

For subjects who are unable to tolerate the toxicities associated with vorinostat treatment, dose reduction should be initiated in an attempt to have the subject complete 2 full cycles of treatment. If the subject is unable to tolerate treatment with vorinostat despite attempts at dose reduction and has not had documented disease progression, the subject may receive KW-0761 after consultation with the Medical Monitor or designee and subsequent approval documentation from the Sponsor.

Drug intolerance is defined as:

- A serious AE attributed to the drug;
- \geq Grade 3 AEs excluding inadequately treated nausea, vomiting and diarrhea and alopecia.

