Comparisons between treatment arms for all other secondary endpoints such as Likert scale, and Itchy QoL will be conducted with no adjustment for multiple comparisons used for those statistical tests. Exploratory subset analyses for PFS and any of the secondary endpoints by region, study site, compartment involvement, CCR4 expression status, disease subtypes, and medical history may be conducted. Details of such subset analyses will be provided in the Statistical Analysis Plan. Although overall survival (OS) is not a secondary endpoint, each subject will be followed in this study for a minimum of 2 years to generate information on OS. Using this follow-up information, a comparison between treatment arms for OS will also be conducted and considered exploratory. Statistical analyses on OS using follow-up data may take place after database lock for the study and will be reported as supplemental to the Clinical Study Report.

Randomization will be stratified within the 2 disease types, SS and MF and 2 disease stages IB or II and III or IV. The efficacy analyses described in this section will be conducted as stratified tests but may also be conducted as a subset analysis within each of these disease-type groups and disease stages. Comparison of endpoints between these 2 groups and

stages will be conducted for each treatment assuming adequate sample sizes in the respective groups.

Exploratory analyses based on other subject groupings and with other parameters may also be conducted.

Since the primary endpoint is PFS, the reference median PFS for vorinostat is assumed to be 169 days. The median PFS for KW-0761 therapy is targeted for 254 days, a 50% improvement over this reference median. For a 24-month accrual and 12 month follow-up on the last subject dosed, [Table 10.3-1](#) gives the power and the number of PFS events required to show superior PFS for KW-0761 therapy over vorinostat at the one-sided 0.025 significance level. The ITT set is used for this primary analysis. The same analysis conducted using the Efficacy Evaluable set is considered secondary.

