Under these assumptions, for the ITT population, a total of 255 PFS events will give 90% power (row is in bold in [Table 10.3-1](#)). For this study, the final primary analysis comparing PFS between treatment groups will not be conducted until 255 PFS events occur or until a maximum of 24 months after the last randomized subject's first dose, whichever comes first. In the event that the study is stopped prior to 255 PFS events are observed, the primary test will be performed at less than 90% power under the current assumptions according to [Table 10.3-1](#).

Each of these calculations uses a log-rank test to compare the 2 survival curves. Sample size calculations were computed using SAS software version 9.3 using PROC POWER, Twosamplesurvival test = logrank.

Table 10.3-1 Required PFS Events and Power for Comparison of PFS Kaplan-Maier Curves Between the Vorinostat and KW-0761 Arms at the 0.025 Level

Vorinostat Median PFS = 169 Days, KW-0761 Median PFS = 254 Days		
Power	Total Required PFS Events	Expected Total Sample Size to Achieve The Required Events
90	255	288
89	247	280
88	239	270
87	231	262
86	225	254
85	218	248
84	212	240
83	206	234
82	201	228
81	196	222
80	191	216

The total sample size of 288 represents the approximate number of subjects that may be necessary for 255 PFS events to occur within the projected 36 months of the trial. If a 10% inflation factor is applied to this total (about 29 subjects) to take into account those subjects that may be lost to follow-up prior to documented progression, a total of 317 enrolled subjects may be necessary in order to observe 255 PFS events.

The observed rates of PFS events, recruitment, and drop-outs will be monitored throughout the study and may be used to alter the number of sites, the accrual period, and the follow-up period to achieve the required 255 PFS events in a timely manner. If the 255 PFS events are not observed within 36 months from the start of enrollment the study will be stopped at approximately 24 months after the last randomized subject's first dose.

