6.11.2.2 Sensitivity Analyses of Primary Efficacy Variable

Three sensitivity analyses will be performed for PFS during randomized treatment period based on the on-site Investigator's assessment and the ITT Set using the following definitions:

- 1) Sensitivity Analysis 1: PFS is defined as the time from the day of randomization to a treatment arm until documented progression in any compartment based on the Investigator's assessment per CTCL response criteria or death due to any cause provided that death is not more than 8 weeks after the last post-baseline tumor assessment or the last dose of study drug (if the subject did not have any post-baseline tumor assessment).

Using this definition, the disease progression reported during the follow-up period would not be considered as an event in the sensitivity analysis, but would be a censored value on the day of the last tumor assessment.

- 2) Sensitivity Analysis 2: PFS is defined as the time from the day of randomization to a treatment arm until the earliest date of documented progression in any compartment based on the Investigator's assessment per CTCL response criteria, or clinical progression at the end of the randomized treatment, or documented disease progression reported during the follow-up period, or death due to any cause.

Using this definition, clinical progression noted at the end of the randomized treatment would be considered as an event in the sensitivity analysis.

- 3) Sensitivity Analysis 3: An additional worst-case sensitivity analysis will be performed based on the ITT Set using the following definition:

PFS is defined as the time from the day of randomization to a treatment arm until documented progression or death due to any cause. The date of documented disease progression will be the earliest date of disease progression in any compartment based on the Investigator's assessment per CTCL response criteria or disease progression reported during the follow-up period. For assessments where progression is reported by the investigator but is **not** confirmed by the IR, the progression date will be set to the last tumor assessment plus one day in the KW-0761 treatment arm and will be censored in the Vorinostat treatment arm.

The same censoring rules as described in Section 6.11.1.1 will be used for the sensitivity analyses.

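### A questionable PD that is never re-evaluated is a non-event in primary PFS and can be censored at the visit that met PD criteria; no sensitivity analysis tests this

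*SAP*

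**What the plan says.** **Event rule.** Protocol 5.2.1.4 and 5.2.2.3 and SAP 3.2.2.3 let a subject who meets PD criteria remain on study until the next evaluation when the investigator doubts the finding clinically. That evaluation is 4 weeks later for skin or blood, and 8 weeks (first year) or 16 weeks (after Year 1) later for nodes or viscera. Below, such a finding is called a held PD. For these subjects SAP 6.11.1.1 states that "the subject is not considered to have progressed unless disease progression is confirmed" at least 4 weeks after the initial date; if it is confirmed, the initial date is the event date. Protocol 10.3 has the same rule. Subjects in frank PD are to stop treatment and are outside it. PD reported in follow-up and death from any cause also count as events.

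**Censoring rule.** A subject without an event is censored at the last post-baseline tumor assessment in any compartment. For new anticancer therapy the SAP adds: "including crossover to KW-0761) in the absence of a PFS event, the PFS time will be censored at the last tumor assessment" before that therapy starts.

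**Crossover.** Protocol 5.3 offers it to vorinostat subjects only: those who "demonstrate progression of disease on treatment with vorinostat at the 8 week (Cycle 2, Day 26-28) assessment, or anytime thereafter, may cross over", after Medical Monitor discussion, sponsor approval and a full disease evaluation.

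**Sensitivity analyses.** SAP 6.11.2.2 defines three and closes: "The same censoring rules as described in Section 6.11.1.1 will be used for the sensitivity analyses".

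**The concern.** A held PD can end in three ways: confirmed, refuted at re-evaluation, or never re-evaluated. The rule gives the last two the same result, so the absence of a second look counts as if it had refuted the first. A held subject may withdraw, stop for toxicity or start another therapy before the compartment is looked at again. The subject is then censored at a date that may be the visit at which PD criteria were met. Censoring tied this closely to progression is unlikely to be independent of the event time.

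Whether a PD is held is the investigator's judgement, in an open-label trial whose primary endpoint is investigator-assessed. Declaring PD can give a vorinostat subject access to KW-0761; a KW-0761 subject has no corresponding option. That is a reason to suspect that holding could be used unequally. If it were, the primary hazard ratio would shift without any drug effect.

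**Working it through.** **1. Design figures, reproduced first.** Inputs: "stratified Log-rank test at the one-sided 2.5% significance level" (SAP 6.11.2.1); "a total of 255 PFS events will give 90% power", "the reference median PFS for vorinostat is assumed to be 169 days" and "The median PFS for KW-0761 therapy is targeted for 254 days, a 50% improvement over this reference median" (protocol 10.3); 24 months of accrual plus 12 months of follow-up; 1:1 allocation.

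- HR = 169/254 = 0.665.
- Schoenfeld events = 4 × (1.960 + 1.282)² / (ln 0.665)² = 254, against 255 stated; power at 255 events is 0.902.
- Exponential event probabilities are 0.929 (vorinostat) and 0.840 (KW-0761), mean 0.8846; 255/0.8846 = 288, as stated; 288 × 1.10 = 317, as stated.

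The design is sound, and the confirmation rule does not change the required number of events.

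**2. Path of a held PD that is never re-evaluated.** It is not confirmed, so it is not an event. A later PD report or death can still supply an event, at a later date. Otherwise the last tumor assessment is the censoring date. For a held skin or blood PD with no further visit, that is the PD visit. For a held nodal or visceral PD it may be a later 4-weekly skin or blood visit, but the compartment in question has still not been re-evaluated. Progression contacts end at alternative therapy (protocol 7.5, SAP 5.5), so the event need not be recovered afterwards.

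**3. Do the sensitivity analyses reach it?** Analysis 1 drops follow-up PD and late deaths. Analysis 2 adds clinical progression at the end of randomized treatment. Analysis 3 penalises KW-0761 where the independent review does not confirm a reported PD. None is defined to count a held PD at its first date.

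**4. Possible size.** The share q of PDs that are held and never counted is not in the documents; the values below are assumptions. If a share q of one arm's PDs is censored at the PD date, that arm's event hazard is multiplied by (1 − q). With true HR 1 and 255 events:

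- apparent HR = (1 − q_KW)/(1 − q_V)
- shift in z = −ln(HR) × √255/2 = −ln(HR) × 7.98
- type I error = P(Z > 1.960 − shift)

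For q_KW = 5% and q_V = 0: shift = 0.0513 × 7.98 = 0.41, and P(Z > 1.55) = 0.061. For 10%: shift = 0.1054 × 7.98 = 0.84, and P(Z > 1.12) = 0.132.

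A log-rank simulation (N = 317, 28-day visits, cut at 255 events, 3,000 runs per scenario) gives the second figure.

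| Assumed scenario | Apparent HR | Type I error, formula | Simulated |
|---|---|---|---|
| No loss | 1.00 | 0.025 | 0.028 |
| 10% lost in both arms | 1.00 | 0.025 | 0.027 |
| 10% KW-0761, 5% vorinostat | 0.947 | 0.063 | not run |
| 5% KW-0761 only | 0.95 | 0.061 | 0.067 |
| 10% KW-0761 only | 0.90 | 0.132 | 0.138 |
| 10% KW-0761 postponed 28 days | – | – | 0.032 |
| 10% KW-0761 postponed 56 days | – | – | 0.042 |

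The Monte Carlo standard error near 0.03 is about √(0.03 × 0.97/3000) = 0.003, so 0.032 is barely distinguishable from the no-loss 0.028. Loss on vorinostat alone works the other way: 5% gives an apparent HR of 1/0.95 = 1.05, against KW-0761.

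**The case against.** A reader might infer that the rule erases PD in the KW-0761 arm only, because PD on vorinostat leads straight to crossover. The documents do not support that. The hold-over provision is worded the same for KW-0761 (protocol 5.2.1.4) and vorinostat (5.2.2.3), and SAP 3.2.2.3 and 6.11.1.1 do not separate the arms. Crossover is optional, needs approval and normally follows two full cycles; nothing exempts a vorinostat subject from being held and re-evaluated. A vorinostat subject with a held PD who crosses over for intolerance is also censored, which removes a vorinostat event. The difference in incentive is a fair inference; a difference in use is not established.

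Nor is every PD without a later visit censored. Only held subjects fall under the rule, and follow-up contacts every 3 months will often turn loss into postponement.

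Partial checks exist. PFS by blinded independent review is a planned secondary analysis, but the reviewer works from the investigator's mSWAT and the SAP does not say whether the confirmation rule applies to the reviewer's dates. Time to treatment failure counts most discontinuations, but it is exploratory and a different endpoint. Sensitivity Analysis 2 may pick up some held subjects who stop for clinical progression.

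Finally, confirmation is prespecified, consistent between the two documents, and has a reason: protocol 5.2.1.8 recognises rash that is hard to tell from lymphoma. That supports disregarding a PD that re-evaluation refutes. It does not support disregarding one that was never re-evaluated.

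**Conclusion.** The point holds for held PDs with no re-evaluation. They are non-events by default, may be censored at the visit that met PD criteria, and no planned analysis shows how much this matters. Size and direction cannot be derived from the documents. One-sided type I error stays at 2.5% if the loss is equal, is about 3-4% if 10% of KW-0761 PDs are only postponed by 28-56 days, and reaches 6.1% or 13.2% only if 5% or 10% are lost permanently from KW-0761 and none from vorinostat. Those last two figures illustrate one assumption; they do not estimate this trial's error rate. This should be fixed before database lock, but it does not by itself invalidate the primary analysis.

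**What to change.** 1. In SAP 6.11.1.1, with protocol 10.3 aligned, state: *A questionable PD is an event at its initial date unless a later evaluation of that compartment, done on randomized treatment, no longer meets PD criteria; if there is no such evaluation, the initial date stands.* Genuine non-confirmation keeps its present effect.
2. Add a PFS sensitivity analysis in which the first assessment meeting PD criteria in any compartment is the event in both arms, whatever the label or later non-confirmation.
3. Tabulate held PDs by arm and outcome: confirmed, refuted, never re-evaluated. This replaces the assumed shares with observed ones.

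Cost: a few more events, one or two more tables, and a small wording change to a prespecified primary definition, to be made before database lock. No change to patient management or to the 255-event target is needed.
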